It is known that OASIs can lead to anal incontinence especially when damage to the anal sphincter is not recognised at the time of delivery (20) (21). The incidence of clinically undetected OASIs has been shown to vary between 13 to 87% (11) (22) (23). Two clinical studies have demonstrated that when a trained doctor re-examined the perineum and anal sphincter that the rate of OASIs doubled (22) (24). This highlights the need to improve education of obstetricians and midwives in perineal anatomy and clinical diagnosis of OASIs. However despite training, doctors and midwives still fail to identify all OASIs (11) (25). Although EAUS can increase the detection rate of OASIs (22), it is not widely available in most UK obstetric units. In contrast, TPUS is available in most obstetric units and we therefore wish to determine whether TPUS in addition to a routine clinical examination will increase the detection rate of OASIs.

Anal incontinence can occur if OASIs are not repaired adequately (26) (27) (28). There is a significant correlation between the extent of an anal sphincter defect and the degree of anal incontinence (29). Ultrasound assessment between one week and one year after primary repair of OASIs has shown that between 16 to 90% (12) (28) (26) (15) (27) (30) have a residual anal sphincter defect. Women with a residual anal sphincter defect have significantly more symptoms of anal incontinence than those without a demonstrable defect (26). It is therefore not unreasonable to assume that some of these residual defects on scans represent injuries that were either not or incompletely repaired at the time of delivery. We therefore wish to investigate whether the use of TPUS immediately after primary repair of OASIs may be able to detect an inadequate repair which will be confirmed at the six to eight weeks follow-up.

The reported rates of anal incontinence following primary repair of OASIs range between 15 and 61% (31). Women with anal incontinence are more likely to have an EAS defect (26). We wish to perform a TPUS at six to eight weeks postpartum to assess the anal sphincter, and determine whether there are differences in the morphology compared to TPUS findings at delivery.

Hiatal dimension and levator ani avulsion

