Computerised models suggest that with the descent of the fetal head that there is distension of the pelvic floor muscles (51). The descent of the fetal head is usually determined by digital vaginal examination (DVE) in relation to the ischial spines and is called the fetal head station (56). This is however a subjective measure but can be measured objectively with TPUS (57) (58) (59) (58) (60). Therefore we wish to investigate changes to the pelvic floor muscles in relation to fetal head station objectively using TPUS.

Forceps delivery (61) (62) (63) (41) (64) (65) (45), prolonged second stage (66) (62) (67) and occipito-posterior (OP) position (33) are risk factors for LAM avulsion. The study evaluating OP with LAM avulsion were done as the baby was being delivered

when one can see the position of the baby's head (33). In labour the diagnosis of OP position was made by a DVE. However there is good evidence that diagnosing the position of the head by DVE can be difficult (68) and that ultrasound diagnosis is more accurate (69) (70) (71). Given that there have been no studies evaluating the position of the fetal head in labour and its relation to LAM avulsion, we propose to accurately diagnose fetal head position in labour and correlate it with LAM avulsion using TPUS.

In summary LAM avulsion and hiatal dimensions are associated with pelvic organ prolapse (45) (46) (47) (34) and both anal (13) (36) (37) (38) and urinary incontinence (39) (32) (40) (41) (42) (43). TPUS can be used to evaluate changes to these muscles in labour and also objectively measure fetal head station and position. This will be the first to study to evaluate these changes during normal labour. Understanding this is important so that preventative strategies can be developed to try and improve the quality of life for women.

HYPOTHESIS

- Transperineal ultrasound at delivery will increase the detection of OASIs.

AIMS OF THE STUDY

Primary Aim

- To determine whether the use of the transperineal ultrasound will improve the detection of OASIs immediately after vaginal delivery.

Secondary Aims

- To measure hiatal dimensions during labour and correlate to levator detachments.
- To correlate intrapartum fetal head position and station identified using three-dimensional (3D) transperineal and transabdominal ultrasound with levator injury.
- To assess anal sphincter integrity immediately after primary repair of OASIs with transperineal ultrasound.

DESIGN AND METHODOLOGY

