Prospective study to be conducted between January 2017 and April 2018 at University Hospital Lewisham. Recruitment will start in January 2017 and stop in April 2018.

Sample identification

All women attending the hospital for routine anomaly ultrasound examinations between 20 and 22 weeks of gestation will be invited to participate and will be given an information leaflet at that stage. The initial approach will be made by a member of the clinical care team when women are admitted for induction of labour or are in labour on the delivery suite and the research team can then approach if the potential participant agrees to be approached. The research fellow (KW) will invite eligible women to participate in the study. The source of identifiable personal information that will be used to identify potential participants will be their maternity notes.

Patients inclusion criteria

The inclusion criteria are:

- women who are undergoing their first vaginal delivery
- 37 weeks of gestation or more
- a singleton pregnancy

- cephalic presentation
- maternal age 18 years old or more and being able to read and understand English.

Patients exclusion criteria

Exclusion criteria are those who do not fit in the inclusion criteria.

Size of sample

Power calculation: The incidence of clinically identified OASIS in nulliparous women is 6%. With increased surveillance with transperineal ultrasound and a detailed examination by a trained doctor we predict the detection rate of OASIS will be 12%. Assuming that 10% of the subjects will have discordant responses, and also assuming a 5% significance level and 80% power, it is calculated that 216 women would be required for the study.

Statistics

Due to the paired binary nature of the data (i.e. two measurements for each subject), the McNemar test will be used for the data analysis.

Method of evaluation

The research fellow (KW) will assess fetal head station and hiatal dimensions by TPUS and fetal head position by transabdominal ultrasound.

Perineal and anal sphincter trauma will be assessed and classified by the accoucher following vaginal delivery. Women will be re-examined by the research doctor (KW) who is trained in performing a detailed vaginal, perineal and rectal examination. When an OASIs is identified by the research fellow that is missed by the accoucher it will be verified by the consultant between 08.00 and 20.30 and by the ST6-7, specialty doctor or consultant out of hours and repaired.

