Secondly TPUS will be performed to assess anal sphincter and hiatal dimension in the immediate postpartum period on all women in the study. TPUS will be repeated after the primary repair of OASIs to check the integrity of the anal sphincter. Images will be stored for independent assessment by experts in TPUS.

A follow-up appointment will be arranged for six to eight weeks later. At follow-up, all patients will be asked to complete a standardised questionnaire including symptoms of anal incontinence according to the St. Mark's Incontinence Score (SMIS) and undergo a repeat TPUS to assess the anal sphincter and hiatal dimensions.

Demographic and obstetric data will be collected prospectively from the maternity notes, including: maternal age, gestational age at delivery, parity, body mass index, history of previous caesarean section, spontaneous or induced labour, duration of first and second stage of labour, indication for operative vaginal delivery, final mode of delivery, mediolateral episiotomy, and neonatal weight. The following ultrasonographic data will also be collected: fetal head position, angle of progression, hiatal dimension, signs of levator avulsion, anal sphincter integrity.

ETHICAL CONSIDERATION

This study is a self-funded project. Information about the study will be given to women during the antenatal period. Those who agree to participate will be consented on admission to labour ward.

CONSENT

Informed consent will be obtained prior to participating. A discussion will be carried out between the potential participants and the research fellow (KW) about the nature and objectives of the study and possible risks associated with their participation. An

opportunity will be given to potential participants to ask questions. Written material (e.g. information leaflet and consent document) will be given.

REGULATORY COMPLIANCE

Before enrolling patients into the study, the chief investigator (KW) will apply for NHS permission from the NHS Research & Development (R&D). If there are any amendments that will potentially affect a site's NHS permission, the chief investigator will confirm with R&D department that NHS permission is on going.

[figure not shown]
PROTOCOL COMPLIANCE

Any accidental protocol deviations will be documented on the relevant forms and reported to the chief investigator.

DATA PROTECTION AND PATIENT CONFIDENTIALITY

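### The primary aim asks what TPUS adds, but the McNemar comparison is sized on TPUS bundled with a trained doctor's re-examination, so a positive result could not be credited to TPUS

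*Protocol*

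**What the plan says.** **Aim.** The Primary Aim is "To determine whether the use of the transperineal ultrasound will improve the detection of OASIs immediately after vaginal delivery". The Background (OASIs section) puts the same question as TPUS on top of the routine clinical examination.

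**Sample size.** The first rate is 6%, the clinically identified incidence in nulliparous women. The second is for a package: "With increased surveillance with transperineal ultrasound and a detailed examination by a trained doctor we predict the detection rate of OASIS will be 12"%. The paragraph continues "Assuming that 10% of the subjects will have discordant responses", with 5% significance and 80% power, and arrives at 216 women.

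**Test.** The Statistics paragraph refers to "two measurements for each subject), the McNemar test will be used for the data analysis". It does not name the two measurements or say what makes one positive.

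**Procedures (Method of evaluation).** The accoucheur classifies the trauma and the research doctor re-examines. Then: "When an OASIs is identified by the research fellow that is missed by the accoucher it will be verified by the consultant" in the daytime, or by other senior staff out of hours. The next paragraph opens "Secondly TPUS will be performed to assess anal sphincter and hiatal dimension in the immediate postpartum period on all women in the study", and later adds "Images will be stored for independent assessment by experts in TPUS". The text does not link the expert reading to the primary count, and does not schedule endoanal ultrasound.

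**Evidence cited.** The Background reports from two clinical studies that "when a trained doctor re-examined the perineum and anal sphincter that the rate of OASIs doubled". It also reports a comparative study in which a defect on TPUS needed further clinical assessment before it could be taken as an OASI. The women in that study were more than 12 months after delivery, so it is only indirect evidence for scans at delivery.

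**The concern.** Two things determine what a significant McNemar result would mean.

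**Attribution.** The aim isolates TPUS, but the only pair the protocol quantifies does not. If the second measurement is TPUS plus re-examination, any gain belongs to the package. The protocol's own background gives the re-examination enough effect to account for the whole planned difference, yet the result would be read as evidence for ultrasound.

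**What counts as a detection.** McNemar compares how often each column is positive. It does not ask whether the positives are right. If a defect seen on TPUS alone enters the table without confirmation, false positives count as improved detection. The verification sentence closes the paragraph on clinical re-examination and comes before TPUS is introduced, so its reach to TPUS-only findings is not clear.

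**Working it through.** **1. The plan's own figure.** Inputs from the Size of sample paragraph: difference d = 0.12 − 0.06 = 0.06; discordant proportion p = 0.10; 5% significance, taken as two-sided; 80% power. With b the proportion positive on the second measurement only and c the proportion positive on the first only:

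- b − c = 0.06 and b + c = 0.10, so b = 0.08 and c = 0.02. Both positive = 0.06 − 0.02 = 0.04.
- N = [1.960·√p + 0.8416·√(p − d²)]² / d² = [1.960·√0.10 + 0.8416·√0.0964]² / 0.0036 = (0.6198 + 0.2613)² / 0.0036 = 215.65, rounded up to **216**.

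The stated figure reproduces. Enumerating all outcomes at n = 216 gives power of 77.0% for the exact McNemar test and 83.8% for the uncorrected chi-square version.

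**2. Attribution.** Suppose the re-examination alone doubles the rate, as the Background reports, and TPUS contributes nothing. Then 6% becomes 2 × 6% = 12%. With the plan's 10% discordance the cells are again b = 0.08 and c = 0.02, and power is again 77% (exact) or 84% (chi-square). The bundled comparison behaves the same whether or not TPUS does anything.

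**3. Unconfirmed TPUS positives.** The protocol gives no specificity for TPUS at delivery, so a range is assumed. True prevalence is taken as the plan's 12%, leaving 0.88 × 216 ≈ 190 women without OASI. The accoucheur is assumed to make no false-positive calls. False positives as a proportion of all women are fp = 0.88 × (1 − specificity).

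The TPUS column is compared with the accoucheur, and any TPUS positive counts. The entries are the chance of a significant result favouring TPUS (exact McNemar, two-sided 5%, n = 216):

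| Assumed specificity | Expected false positives | (a) No net true gain: b = 0.02 + fp, c = 0.02 | (b) TPUS only loses true cases: b = fp, c = 0.02 | (c) True net gain of 2 points: b = 0.04 + fp, c = 0.02 |
|---|---|---|---|---|
| 100% | 0 | 1% | 0% | 15% |
| 99% | 1.9 | 4% | 0% | 28% |
| 98% | 3.8 | 12% | 1% | 43% |
| 97% | 5.7 | 24% | 3% | 58% |
| 95% | 9.5 | 54% | 20% | 81% |

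The reverse cell of 2% is the one the plan implies. With the uncorrected chi-square test, column (a) at 97% is 32% instead of 24%. A false-positive rate of 0.06/0.88 = 6.8% would by itself produce the whole planned rise of 6 points.

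**4. Power for a confirmed count.** With c = 0.02 and a confirmed net gain of 6, 5 or 4 points, exact power at 216 is 77%, 64% or 47% (chi-square 84%, 72% or 57%).

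**The case against.** **Verification may already cover TPUS findings.** The sentence applies to any OASI the research fellow identifies and the accoucheur missed, without limiting how it was found. The aim counts OASIs, and the Background distinguishes a TPUS defect from an OASI. This is a fair reading, and if it is the intended one the false-positive problem largely disappears. The study flow chart is not shown and may settle the matter. A reader might infer that TPUS positives are counted with no confirmation at all. The documents do not support that; they support only that the text is unclear. Clear verification would still leave the attribution problem, because it does not separate the scan from the re-examination.

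**This belongs in the SAP.** Coding of positives often does. But the protocol has already fixed the test and the sample size on a 12% that does not match its aim. Whether a TPUS-only finding is verified is a procedure at delivery that cannot be added at analysis.

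**The sizes in step 3 rest on assumptions.** This stands. No specificity is given. Scenarios (a) and (b) imply TPUS sensitivity of 50% (0.06/0.12) and 33% (0.04/0.12). The Background cites a study with 70% for external and all internal sphincter defects, in a different population. At 99% specificity the effect in (a) is small. In (c) there is a true gain, so significance there is not a false conclusion. The table shows what could happen and does not forecast it.

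**Clinical confirmation is itself imperfect.** This also stands. The Background says trained staff still miss some OASIs, so an unconfirmed TPUS positive is not a proven false positive.

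**Conclusion.** The protocol is inconsistent about its primary comparison: the aim is TPUS added to routine examination, while the powered comparison is TPUS plus re-examination. By the protocol's own background figure, the bundled comparison would reach its planned power (77% exact, 84% chi-square) with TPUS adding nothing. This part needs no assumption beyond the document, except that the reported doubling carries over to this setting.

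The confirmation issue is secondary and conditional. It matters only if TPUS-only positives are counted unverified. In the no-net-gain case its size then runs from about 4% to 54% over assumed specificities of 99% to 95%.

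A reader might also infer that 216 is wrong. It is not: it follows from the stated inputs. What needs qualifying is that the 80% power belongs to the bundled 6% versus 12% comparison and not to TPUS alone. This should be fixed, with medium confidence given the missing flow chart.

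**What to change.** - Name the two paired measurements in the Statistics section so that they match the primary aim.
- Record the accoucheur, re-examination and TPUS results as three separate items per woman, so that the gain from TPUS can be told apart from the gain from re-examination. The stated order of procedures already allows this.
- Use confirmed OASIs as the primary count in both columns. Report TPUS-positive, unconfirmed women alongside as their own count, neither as detections nor as proven false positives.
- Reconcile the two paragraphs of Method of evaluation on whether the planned senior verification covers TPUS-only findings. If it does not, state that TPUS cannot exceed the re-examination on the confirmed count.
- Keep 216, but describe its 80% power as applying to the bundled 6% versus 12% comparison.

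**Cost.** Mainly wording, plus one extra reported count. If verification is stated to cover TPUS-only findings, some extra senior examinations follow. The clinical reference remains imperfect, and no senior verification is stated for women the accoucheur calls positive, so their status rests on the re-examination. Power falls if the confirmed gain is below 6 points, as step 4 of the working shows.

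### Does checking only the tears that the accoucher missed undermine the McNemar comparison and the sample size of 216?

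*Protocol*

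**What the plan says.** Under Size of sample the protocol gives the inputs. "The incidence of clinically identified OASIS in nulliparous women is 6" per cent; with ultrasound and a detailed examination by a trained doctor, "we predict the detection rate of OASIS will be 12" per cent. On disagreement between the two assessments the text reads: "Assuming that 10% of the subjects will have discordant responses". The error rates come next ("also assuming a 5% significance level and 80% power"), and the outcome of the calculation is given as follows: "it is calculated that 216 women would be required for the study". Under Statistics the data are described as paired and binary, and "the McNemar test will be used for the data analysis".

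Under Method of evaluation the accoucher classifies the trauma and the research doctor then re-examines the women. "When an OASIs is identified by the research fellow that is missed by the accoucher it will be verified by the consultant" in the daytime, or by other named doctors out of hours, and the tear is then repaired. Transperineal ultrasound (TPUS) is done in every woman, and the stored images are read independently. Nothing is said about checking a tear that the accoucher diagnosed and the research assessment did not find.

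The Background states the question as an add-on: "we therefore wish to determine whether TPUS in addition to a routine clinical examination will increase the detection rate of OASIs".

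**The concern.** McNemar's test uses only the women on whom the two assessments disagree. If a senior filters one discordant cell and not the other, false positives are removed from the research side alone, and the difference between the cells no longer compares like with like. The protocol's own inputs expect women in the unfiltered cell: 2 of the accoucher's 6 percentage points, a third of the accoucher's diagnoses, would be contradicted by the research assessment with no stated way to settle them.

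The add-on wording in the Background raises a second doubt. If every accoucher diagnosis counted automatically as a detection under the combined strategy, the lost cell would be empty and discordance would equal the 6-point difference. The assumed 10% would then belong to a different table.

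At stake would be the power of the primary comparison and the meaning of its result. A confirmation not obtained at delivery could not be recovered later.

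**Working it through.** **Inputs.** From Size of sample: 6% and 12% detected, 10% discordant, 5% significance, 80% power, n = 216. The test is taken as two-sided; the protocol does not say so, but this reading reproduces 216 and a one-sided test does not (169.6).

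**Step 1, the two cells.** Let b be the gained proportion (accoucher negative, research positive) and c the lost proportion (the reverse).

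- b − c = 0.12 − 0.06 = 0.06 and b + c = 0.10.
- So b = 0.08 and c = 0.02.
- In 216 women: 216 × 0.08 = 17.3 and 216 × 0.02 = 4.3.

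**Step 2, the protocol's figure.** With d = b − c and p = b + c, the unconditional McNemar formula is

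n = [1.960 √p + 0.8416 √(p − d²)]² / d²

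- 1.960 × √0.10 = 0.6198
- 0.8416 × √(0.10 − 0.0036) = 0.2613
- (0.6198 + 0.2613)² / 0.0036 = 0.7763 / 0.0036 = 215.65, so 216.

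Formula power at 216 is 80.1%. Inputs, test and sample size agree.

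**Step 3, one-sided filtering.** Suppose that only confirmed findings are analysed, that the 12% is a rate before confirmation, and that seniors confirm a share f of the gained cases. The values of f are assumptions; the protocol gives none. Formula power at n = 216 is Φ[(d√n − 1.960√p) / √(p − d²)].

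| f | b | Difference (c = 0.02) | Power, only gained cell filtered | Power, both cells scaled by f |
|---|---|---|---|---|
| 1.00 | 0.080 | 6.0 points | 80% | 80% |
| 0.90 | 0.072 | 5.2 points | 72% | 76% |
| 0.75 | 0.060 | 4.0 points | 55% | 68% |
| 0.60 | 0.048 | 2.8 points | 35% | 58% |

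Only the gap between the last two columns is due to the one-sidedness: 4, 13 and 23 points. The rest of the fall would occur under symmetric checking too.

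**Step 4, the add-on reading.** With b = 0.06 and c = 0 the formula gives n = 128.4, so 129, and 95.5% power at 216. The exact binomial test gives 99.1% at 216 but 79.2% at 129, just short of 80%. (For the protocol's own cells of 8% and 2% the exact test gives 77.0% at 216.) On either method, 216 women would be more than this reading needs.

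**Step 5, what the text supports.** Step 3 needs two premises. The sentence on verification ends in repair, so it reads as a clinical step before suturing and does not define the analysed result. The 12% is called a predicted detection rate, with no word on whether it is before or after confirmation. Step 4 needs a rule that either positive counts. No such rule is written. Size of sample sets the routine rate against ultrasound plus a trained doctor's examination, re-examination is not limited to women whom the accoucher called negative, and every woman is scanned. A lost cell of 2% can therefore occur.

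**The case for a change.** The strongest case for a change is that raw positives are a poor outcome here. The Background itself reports that a defect seen on TPUS needs further clinical assessment before an injury is accepted, so an aim of improving detection seems to call for confirmed tears. The protocol then confirms in one direction only. Adding the reverse check would concern about four women and use seniors already on duty.

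Part of this stands. Verification is written for one direction only, and the protocol does not say whether raw or confirmed findings fill the table, nor how a woman called positive by the accoucher and negative by the research assessment is coded.

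The rest does not carry. If raw classifications are analysed, both cells are on the same footing and the power loss disappears. If confirmed tears are analysed and the 12% already means confirmed tears, Step 3 deducts the same loss twice. If neither holds, filtering only the research side pulls the difference towards zero, which is conservative for the hypothesis that TPUS raises detection. The reverse check is also not free: it adds an examination, by a further examiner, for women whom the protocol does not send for one.

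**Conclusion.** No change is called for. The sample size is correct for its stated inputs (215.65, rounded up to 216) and describes the named test. The possible effects point in opposite directions: power falls to 72%, 55% or 35% under assumed confirmation rates of 90%, 75% or 60%, or rises to 95.5% by the formula (99.1% exact) if the lost cell is empty. Each depends on a premise that the protocol does not state, so no net error is shown. Restating discordance as 6% would correct no figure shown to be wrong.

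What remains is a coding detail of the primary table: raw or confirmed findings, and the handling of about four women. A SAP commonly fixes this, and none is at hand. Analysts can fill it sensibly by entering each assessor's own classification in both cells and reporting the verified findings beside it. This conclusion assumes that each assessor's classification is recorded as made, which the sequence under Method of evaluation allows.
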